### **5c. Qualitative Arm**

An assumption of qualitative research is that no pre-determined hypothesis is made. Following autologous stem cell treatment for chronic lung disease, patients will report improvement in at least one of several quality of life indicators.

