## **2a. Situating the Researcher**

[name] is a doctorally-prepared Family Nurse Practitioner certified by the American Nurses Credentialing Center and licensed to practice in the state of Texas. A member of the Southern Nursing Research Association, [name] has experience designing and conducting qualitative and quantitative research and mixed-methods studies. Her doctoral dissertation was a qualitative study involving a marginalized population of drug-addicted women ([name], 2013). She has also done pilot work on a population of incarcerated women using quantitative methods. [name] has a current manuscript pending review on using the interpretive phenomenological inquiry method for qualitative research. [name] is well-experienced in the protection of human research subjects. She is an expert in the promoting rigor in qualitative research design and situating its importance in medical research.

[name] is a nationally certified and practicing Family Nurse Practitioner. In addition to her research role, [name] will be the primary clinician at the research site, providing physical assessments, reviewing patient medical records and formulating the patient plan of care. Because each patient of the Lung Institute is treated using the same protocols (there are no control groups), this minimizes the conflict of interest, randomization and blinding that must occur with experimental studies.

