## 6. STUDY DESIGN

This study uses a concurrent mixed-methods approach to collect and analyze both qualitative and quantitative data. The *quantitative* arm will use a non-experimental, descriptive approach to measure and analyze pre- and post-stem cell treatment pulmonary function test results of treated patients. Measurement of the occurrence of adverse events will also be part of the quantitative arm.

Pre-treatment pulmonary function test results (measured by FEV1) will be compared with a six-month post-treatment pulmonary function test result (FEV1) for each patient. The aim of this method is to generalize an improvement in pulmonary function (measured by FEV1) among the general population of all individuals treated by autologous cell therapy for chronic lung disease.

The *qualitative* arm of the study uses an interpretive phenomenological approach to collect and analyze pre- and post- cell therapy anecdotal data regarding perceived quality of life among treated patients. Phenomenological research involves investigating the lived experience.

Qualitative research has several assumptions (D. Nicholls, 2009; Ritchie & Lewis, 2003). Primarily, there is no predetermined theoretical framework- rather the theory, if any, is derived from the data. Secondly, qualitative research is context-driven. Finally, qualitative researchers focus on the *emic* perspective that concerns itself with the view, perspectives and descriptions of others.

This study uses an *interpretive phenomenological analysis* (IPA) approach throughout the study from planning to data collection to analysis. This methodology is used to illuminate each participant's variation of the same general phenomenon (in this case, COPD) (Reissman, 2008; Ritchie & Lewis, 2003).

Data from both arms of the study will be combined following data collection for analysis, discussion and presentation. Safety data on adverse outcomes will be tracked and reported separately as a descriptive, quantitative analysis.

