## 10. STUDY OUTCOMES

The anticipated outcomes of this study are a minimization of adverse events, an improvement in pulmonary function testing (measured by FEV1), and an improvement in self-reported quality of life indicators.

Rev\_2/5/16 Page 5 of 10

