### **12b. Statistical methods**

For the quantitative, descriptive arm of this study, sample characteristics will be collected to include age, sex and diagnosis. Pre- and post-treatment FEV1 measurements will be collected on each patient and evaluated by simple measures of central tendency (mean, median and mode). Sufficient descriptive data will be collected and reported to encourage replication of our study.

For the qualitative, anecdotal arm of the study, Lung Institute utilizes CCQ, the Clinical COPD Questionnaire to document patient's perceptions on improved quality of life. The information will be collected and interpreted by evaluating for common themes within the anecdotes. As a note regarding the rigor of qualitative research: is important in qualitative research to ensure that the study is credible and trustworthy (Smith, Flowers and Larkin, 2009). A number of guidelines for assessing this quality look toward establishing credibility. Psychologist Lucy Yardley's work in 2000 provides the principles for assessing the quality of qualitative research and how the interpretive phenomenological method can address them. First, the study must provide good *sensitivity to context*. In this study, the immersion in the clinic through field experience, the existing literature on COPD and stem cell treatment, and the anecdotes obtained

Rev\_2/5/16 Page 7 of 10

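### Section 5c disclaims a hypothesis, then predicts improvement on any one undefined indicator, and no rule requires unchanged or worsened quality of life to be reported

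*Combined protocol and SAP*

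**What the plan says.** Section 5c (Qualitative Arm) consists of two sentences. The first is "An assumption of qualitative research is that no pre-determined hypothesis is made". The second predicts that after treatment "patients will report improvement in at least one of several quality of life indicators". The indicators, their number, the time point and the amount of change that counts are not given. Section 6 (Study Design) takes the same line as the first sentence: "there is no predetermined theoretical framework- rather the theory, if any, is derived from the data".

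Section 10 (Study Outcomes) anticipates "an improvement in self-reported quality of life indicators". Section 12b (Statistical methods) says that the clinic uses "the Clinical COPD Questionnaire to document patient's perceptions on improved quality of life", and that the information will be "interpreted by evaluating for common themes within the anecdotes". No section says how an account of worsening or of no change is to be classified, counted or reported.

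Other parts are neutral in direction:

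- Section 3 aims to describe changes in quality of life.
- Research question 3 in section 4 can be answered no.
- Section 6 collects accounts of perceived quality of life before and after treatment.
- Section 11 measures quality of life at 2 weeks, 3 months and 6 months and gives each patient a journal of how they feel.
- The Office Manager SOP (step 3) takes a quality of life survey at first-day check-in, and the A-ASC Procedures policy (section H) seeks one at six months.

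**The concern.** Two statements that cannot both govern the same arm stand next to each other in 5c. If the second prevails, it works as the arm's expectation, and it is a lenient one: a single better indicator suffices, whatever happened to the others. Section 12b then names improvement as the thing to be documented, with no matching instruction for the other two directions.

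At stake is the answer to research question 3. A patient who is better on one aspect and worse on the rest agrees with the stated expectation, and nothing obliges the report to show the rest. There is no control group and, by section 11b, no masking of those who assess or analyse outcomes, so the design does not offset the slant. The risk is concrete: sections 1 and 2 summarise the pilot work by one figure, 84 percent improved, with no share unchanged or worsened beside it. The present wording would allow the same format for the planned 200 patients.

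**Working it through.** The plan gives no figure to reproduce here. The sample size of 200 in section 12a has no derivation, and this point does not depend on it. The main check is therefore a comparison of the text.

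**Step 1: direction at each stage.**

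| Stage | Where | Direction |
|---|---|---|
| Aim, research question | Sections 3, 4 | Neutral |
| Collection | Sections 6, 11; SOP and policy surveys | Neutral |
| Hypothesis | Section 5c | Disclaimed, then improvement |
| Anticipated outcome | Section 10 | Improvement |
| Purpose of the CCQ | Section 12b | Improvement |
| Theme analysis | Section 12b | No direction stated |
| Reporting of unchanged or worse | None found | No rule |

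The data can show decline. The gap opens at the hypothesis and stays open through analysis and reporting.

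**Step 2: how easily the 5c expectation is met.** This is an illustration. The documents give neither the number of indicators k nor any rates, so all of these are assumptions. Suppose that there is no true change, that each indicator is called better with probability b and worse with probability w, and that indicators are independent. Then

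- P(at least one better) = 1 − (1 − b)^k
- P(at least one better and at least one worse) = 1 − (1 − b)^k − (1 − w)^k + (1 − b − w)^k

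With b = w = 0.3:

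- k = 3: 1 − 0.343 = 66% better on at least one; 1 − 0.686 + 0.064 = 38% both better and worse on something.
- k = 5: 1 − 0.168 = 83%; 1 − 0.336 + 0.010 = 67%.
- k = 10: 1 − 0.028 = 97%; 1 − 0.056 + 0.0001 = 94%.

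Because b = w was chosen, the share worse on at least one equals the share better on at least one. Only the latter corresponds to the wording of 5c.

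**Step 3: range over the assumed rate, still with independence.** P(at least one better):

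| b | k = 3 | k = 5 | k = 10 |
|---|---|---|---|
| 0.2 | 49% | 67% | 89% |
| 1/3 | 70% | 87% | 98% |
| 0.5 | 88% | 97% | 99.9% |

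**Step 4: worse overall, yet meeting 5c.** With better, same and worse at 1/3 each, the share with more indicators worse than better but at least one better is 11%, 27% and 41% for k = 3, 5 and 10. For k = 3 the only such pattern is one better and two worse: 3 arrangements × (1/3)^3 = 3/27 = 11%.

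**Step 5: the other extreme.** If all indicators move together, P(at least one better) is simply b. The 30% case stays at 30% for any k, and nobody is both better and worse. Real indicators lie between the two extremes, so independence gives the high end.

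**The case against.** A reader might infer that the qualitative arm has no place for worsening and can only confirm benefit. The documents do not support that. Section 12b does not restrict itself to improvement; surveys before and after treatment, open journals and theme analysis can all record decline; and research question 3 can be answered no.

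A reader might also infer that direction is built into the coding. There is no codebook. The one stated method, looking for common themes, has no direction, and no section makes 5c a formal success criterion or says that a per-patient count will be made. Adverse events are collected at the same contacts and reported separately, so some deterioration could surface there, though a decline in quality of life need not be an adverse event. The discussion of rigour in 12b asks for a complete analysis and described steps. That is general and does not supply the missing rule.

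A third inference is that the treating clinician interprets the accounts. Section 2a says that the researcher "will be the primary clinician at the research site", which makes this plausible, but the plan does not name who does the interpretation.

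Finally, the percentages use invented rates and numbers of indicators. The questionnaire is cited as attached in section 11c but is not in the text available, so its items and scoring could not be checked; that is not a fault of the plan.

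All of this stands against the stronger readings. It leaves untouched the contradiction in 5c, the wording of 12b, and the absence of a reporting rule.

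**Conclusion.** The point holds as one about wording and reporting, and it should be fixed. Section 5c contradicts itself. Its prediction is undefined and can be met by a patient who is worse overall. Section 12b frames the CCQ around improvement, and nothing requires unchanged or worsened accounts to be reported. Analysis and reporting for research question 3 are therefore tilted towards benefit, although collection is not.

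The size of the tilt cannot be estimated from the documents. Under the assumed rates, 30% to 97% of patients would meet the 5c wording with no true change at a 30% rate per indicator, from perfect correlation to ten independent indicators. Those figures show that the criterion can be lenient. They do not forecast this study's result. The conclusion rests on the text and would stand without them.

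**What to change.** - **Section 5c:** delete the directional sentence, or move it to the quantitative hypotheses as a statement about a named CCQ score at a stated time point with a stated threshold for improvement. Moving it without those three elements would leave it undefined.
- **Section 12b:** replace "perceptions on improved quality of life" with *perceived change in quality of life (improved, unchanged or worsened)*.
- **Reporting of the survey:** at each follow-up contact, tabulate the numbers improved, unchanged, worsened and missing side by side, with the number of patients treated as denominator. Fix in advance the rule that separates the first three. The missing column matters because section 11 makes the follow-up calls voluntary and the policy limits them to two attempts.
- **Reporting of themes:** present themes of worsening or no change alongside themes of improvement.

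This draws on data the plan already intends to collect and does not require counts from the phenomenological analysis. It assumes that the quality of life survey in the SOPs is the CCQ, which the documents do not state outright. It also needs confirmation that the survey is used at 2 weeks and 3 months, since the policy names it only at six months.

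The cost is some protocol wording and a small tabulation: at most 200 × 3 = 600 classifications, shown in a table of 3 contacts by 4 categories. The downside for the sponsor is that the share improved will look less favourable next to the shares worsened and missing.

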## 6. STUDY DESIGN

This study uses a concurrent mixed-methods approach to collect and analyze both qualitative and quantitative data. The *quantitative* arm will use a non-experimental, descriptive approach to measure and analyze pre- and post-stem cell treatment pulmonary function test results of treated patients. Measurement of the occurrence of adverse events will also be part of the quantitative arm.

Pre-treatment pulmonary function test results (measured by FEV1) will be compared with a six-month post-treatment pulmonary function test result (FEV1) for each patient. The aim of this method is to generalize an improvement in pulmonary function (measured by FEV1) among the general population of all individuals treated by autologous cell therapy for chronic lung disease.

The *qualitative* arm of the study uses an interpretive phenomenological approach to collect and analyze pre- and post- cell therapy anecdotal data regarding perceived quality of life among treated patients. Phenomenological research involves investigating the lived experience.

Qualitative research has several assumptions (D. Nicholls, 2009; Ritchie & Lewis, 2003). Primarily, there is no predetermined theoretical framework- rather the theory, if any, is derived from the data. Secondly, qualitative research is context-driven. Finally, qualitative researchers focus on the *emic* perspective that concerns itself with the view, perspectives and descriptions of others.

This study uses an *interpretive phenomenological analysis* (IPA) approach throughout the study from planning to data collection to analysis. This methodology is used to illuminate each participant's variation of the same general phenomenon (in this case, COPD) (Reissman, 2008; Ritchie & Lewis, 2003).

Data from both arms of the study will be combined following data collection for analysis, discussion and presentation. Safety data on adverse outcomes will be tracked and reported separately as a descriptive, quantitative analysis.

## 7. STUDY SETTING/LOCATION

The study will be conducted at:

## 8. STUDY POPULATION

Lung Institute Dallas  
[name]  
[name]

Populations that may participate vary by selected treatment of those offered by the Lung Institute. Candidates are eligible for treatment if they are diagnosed with Chronic Obstructive Pulmonary Disease and are not excluded by one or more of several disqualifiers that vary by treatment type offered by the Lung institute.

Rev\_2/5/16 Page 3 of 10

### Research Protocol Lung Institute Dallas

Populations diagnosed with COPD were estimated in 2012 to be:

- Nationally: 15,340,484
- Texas: 984,708
- Dallas County: 87,305
- Denton County: 24,614

- Collin County : 30,285

## 9. ELIGIBILITY CRITERIA

Inclusion and exclusion criteria are standards that have been set to determine whether a person may or may not be allowed to enter our study. They are used to identify appropriate participants and to ensure their safety.

### 9a. Inclusion criteria

The community eligible for treatment with the Lung Institute are those diagnosed with COPD and ILD. Populations diagnosed with COPD were estimated by the American Lung Association in 2012 to be:

- US: 15,340,484
- Texas : 984,708
- Dallas County : 87,305
- Denton County : 24,614
- Collin County: 30,285

### 9b. Exclusion criteria

Exclusions from **ALL** Procedures:

- Populations
  - Inability to give informed consent (a diminished understanding or comprehension);
  - Inability to travel to Outpatient Facility;
  - Pregnant women;
  - Prisoners; and
  - Children, under the age of 16 years old
- Active Smoker - Active smoking prevalence has been estimated at:
  - Nationally: 17.8 %
  - Texas: 15.9 %
  - Dallas County: 15.3 %
  - Denton County: 10.1 %
  - Collin County: 9.7 %
- Currently diagnosed with cancer or have had cancer within the past 5 years.
  - Current cancer prevalence is estimated by the National Cancer Institute at 3.7% for males in Texas and 3.9% for females in Texas. National cancer cases were estimated in 2010 to be 13,772,000 nationally for a prevalence rate of 4.5% of the estimated national population of 309,300,000.
- Identification of new nodules/masses per chest x-ray/CT scan report that have not been noted as stable.
  - Documentation of stability must be received for confirmation prior to treatment.
- Active Infection (pulmonary or other);
- Active Tuberculosis
- A History of Recent Hospitalization (requiring mechanical ventilation in a period of one month before treatment);
- End Stage Kidney Failure;
- Acute Heart Failure; and/or
- Other Condition(s) the Provider or Principal Investigator feels would interfere with treatment protocols.

Rev\_2/5/16 Page 4 of 10

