The hypothesized outcomes of Lung Institute therapy are safety and minimization of adverse events, a perceived improvement in the patient's lung condition (to be determined by their ability to be more physically active; walking greater distances with or without oxygen and improved quality of life scales), an improvement in their FEV1 5-10% or more, the ability to reduce their use of oxygen and possibly to stop it., the ability to function well without the use of rescue inhalers, reduction or ceasing of secondary pulmonary infections, reduction in emergency room visits and hospitalizations related to their disease, and an improvement in their six minute walk test.

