## **5. HYPOTHESES**

### **5a. Primary Hypothesis/Quantitative Arm**

Null hypothesis: Following autologous stem cell treatment for chronic lung disease, patients will have no improvement in pulmonary function (measured by FEV1) at six months

Alternative hypothesis: Following autologous stem cell treatment for chronic lung disease, patients will have an increase in pulmonary function (measured by FEV1) of 5 to 10% or more

Rev\_2/5/16 Page 2 of 10

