**2. RULE-OUTS FOR *VENOUS* PROCEDURE**

- a) ACTIVE TUBERCULOSIS;
- b) HISTORY OF CANCER (WITHIN THE PAST 5 YEARS);
  - i. ON A CASE-BY-CASE BASIS, PROVIDER MAY APPROVE PROCEDURE(S) FOR NON-AGGRESSIVE/NON-ACTIVE CASE(S).
- c) IDENTIFICATION OF NEW NODULES/MASSES PER CHEST X-RAY/CT SCAN REPORT THAT HAVE NOT BEEN NOTED AS STABLE.
  - i. DOCUMENTATION OF STABILITY MUST BE RECEIVED FOR CONFIRMATION PRIOR TO TREATMENT.
- d) ACTIVE INFECTION (PULMONARY OR OTHER);
- e) A HISTORY OF RECENT HOSPITALIZATION (REQUIRING MECHANICAL VENTILATION IN A PERIOD OF ONE MONTH BEFORE TREATMENT);
- f) END STAGE KIDNEY FAILURE;
- g) ACUTE HEART FAILURE; AND/OR
- h) OTHER CONDITION(S) THE PROVIDER OR PRINCIPAL INVESTIGATOR FEELS WOULD INTERFERE WITH TREATMENT PROTOCOLS.

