
10.
	
Clinic Staff conducts introductions, reviews process, and checks for Patient readiness.
 
 
• Has Clinic Staff introduced themselves? 
 
✓ Name and Roles
 
 
 
• Has Clinic Staff reviewed the procedure process for the day? 
 
✓ Go over what the Patient can expect during the days procedure
 
 
 
• Has Clinic Staff ensured Patient readiness? 
 
✓ Answer any questions the Patient may have; and
 
✓ Check to see if Patient needs to use the restroom prior to procedure.
 
 
 
 
➤ If NO > Step must be completed prior to proceeding.
 
➤ If YES > Proceed to Step 11 of this SOP

11.
	
Clinic Staff obtains vitals.
 
 
• Has Clinic Staff obtained the following vitals? 
 
✓ Blood Pressure;
 
✓ Pulse;
 
✓ Heart Rate;
 
✓ Respiratory Levels;
 
✓ SaO Levels;
 
✓ EKG (If required, per Practitioner's judgement); and
 
✓ PFT (May be obtained within the 3 days of scheduled treatment)
 
 
 
 
➤ If NO > Obtaining Patient vitals is required prior to proceeding.
 
➤ If YES > Proceed to Step 12 of this SOP

12.
	
Clinic Staff completed the subjective/chief complaint.
 
 
• Has Clinic Staff completed the Subjective/Chief Complaint? 
 
✓ Patient Complaint/Primary Reason for Visit (i.e.: Patient here for shortness of breath, second day of procedure, COPD Treatment, etc.)
 
 
 
 
➤ If NO > Step must be completed prior to proceeding.
 
➤ If YES > Proceed to Step 13 of this SOP

10Mar2016 - version 2.0

LI-001

13.
	
Is today the first treatment day for the Patient?
 
➤ If NO > Proceed to Step 16 of this SOP
 
➤ If YES > Proceed to Step 14 of this SOP

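### Patients just past a non-ventilated exacerbation can enter with a low baseline FEV1, and the plan cannot separate their recovery from a treatment effect

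*Combined protocol and SAP*

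**What the plan says.** Eligibility: Protocol section 9b excludes "A History of Recent Hospitalization (requiring mechanical ventilation in a period of one month before treatment". CL-005 section B repeats the rule for the venous procedure ("A HISTORY OF RECENT HOSPITALIZATION (REQUIRING MECHANICAL VENTILATION IN A PERIOD OF ONE MONTH BEFORE TREATMENT") and, in the same words, for bone marrow. Section 9b also excludes "Active Infection (pulmonary or other", acute heart failure, and "Other Condition(s) the Provider or Principal Investigator feels would interfere with treatment protocols". None of these sets a recovery interval after an episode has resolved.

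Baseline measurement: both procedure SOPs list lung function with the treatment-day vitals (Venous Step 11, Bone Marrow Step 9): "PFT (May be obtained within the 3 days of scheduled treatment". No second baseline test is required to show that a patient is stable.

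Comparison: section 6 states that "Pre-treatment pulmonary function test results (measured by FEV1) will be compared with a six-month post-treatment pulmonary function test result (FEV1) for each patient". Section 2a says there are no control groups, section 11b that everyone is treated, and section 11a that patients refer themselves. The alternative hypothesis in section 5a is that "patients will have an increase in pulmonary function (measured by FEV1) of 5 to 10% or more"; the null is no improvement.

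Analysis: section 12b names age, sex and diagnosis as sample characteristics and summarises FEV1 by mean, median and mode. It has no breakdown by recent exacerbation.

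**The concern.** A patient sent home a week ago after a non-ventilated exacerbation, with no infection still active, meets the written criteria. If FEV1 has not fully recovered when the baseline test is done, the later return to the usual level is counted as improvement. A control group would show the same recovery and cancel it; this design has none.

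The protocol expects such events in its population. Among its hoped-for results the Introduction lists "reduction in emergency room visits and hospitalizations related to their disease", together with fewer secondary infections. Patients choose when to come forward, and it is plausible, though not documented, that they do so when they feel worse. The six-month test is set by the calendar. That asymmetry would push the mean FEV1 change upward, towards the primary alternative, with no treatment effect. Section 6 intends to generalise any improvement to all patients treated this way, so calling the quantitative arm descriptive does not remove the problem.

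**Working it through.** **Inputs.** From the documents: one arm, a pre-treatment FEV1 and a six-month FEV1 per patient, a target of 5 to 10% or more, and an anticipated 200 patients. They give neither the share of recently exacerbated patients nor their FEV1 deficit, so there is no figure of the plan's own to reproduce. The following are assumptions:

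- f0, share with a depressed baseline: 10-30%
- d, their deficit relative to stable FEV1: 10-25%
- f6, share depressed by the same d at six months, independently of baseline status: from 0 to f0
- full recovery otherwise, no treatment effect, no underlying decline

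**Formula.** An affected patient who recovers fully gains d/(1−d) relative to baseline. The average per-patient percentage change is (1 − f6·d) × (1 + f0·d/(1−d)) − 1. With f6 = 0 this reduces to f0·d/(1−d).

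| f0 | d | None affected at six months (points) | Same share affected at six months (points) |
|---|---|---|---|
| 10% | 10% | 0.10 × 0.10/0.90 = 1.1 | 0.99 × 1.0111 − 1 = 0.1 |
| 20% | 15% | 0.20 × 0.15/0.85 = 3.5 | 0.97 × 1.0353 − 1 = 0.4 |
| 20% | 20% | 0.20 × 0.20/0.80 = 5.0 | 0.96 × 1.05 − 1 = 0.8 |
| 30% | 25% | 0.30 × 0.25/0.75 = 10.0 | 0.925 × 1.10 − 1 = 1.8 |

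Between the extremes, with f0 = 20%, d = 15% and f6 = 10%: 0.985 × 1.0353 − 1 = 2.0 points.

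**What drives it.** With equal shares, mean FEV1 in litres is lowered by the same factor (1 − f0·d) at both times and does not change. The remaining 0.1 to 1.8 points come from averaging individual percentages. Material bias therefore needs an excess of affected patients at baseline.

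**What a 5-point mean would take.** With f6 = 0, f0 must be 5 ÷ [100·d/(1−d)]: 45% at d = 10%, 28% at 15%, 20% at 20%, 15% at 25%. Only the upper part of the assumed range gets there.

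**Why a smaller shift still matters.** The null is no improvement, so the shift need not reach 5%. For illustration, assume a standard deviation of change of 15%. With 200 patients the 95% half-width is 1.96 × 15/√200 = 2.1 points, and a spurious mean of 3% would be declared above zero by a two-sided 5% test with probability 0.81 (0.99 at SD 10%, 0.56 at SD 20%). The plan specifies no such test. For individuals, at SD 10% with no treatment effect, 30.9% of patients gain at least 5% by variation alone; if 20% of patients also recover by 10%, this becomes 0.8 × 30.9% + 0.2 × 69.1% = 38.5%.

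**The case against.** Several points on the other side stand.

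- A reader might infer that recovery alone would produce an improvement of the size the trial targets. The documents do not support that. Both inputs are assumed, the middle case of 3.5 points is below 5%, and the larger figures assume that nobody is affected at six months. The progressive loss of lung function that the Introduction describes would also act in the opposite direction.
- A reader might infer that ventilated hospitalization is the only stability rule. It is not: active infection, acute heart failure and provider judgement remove some unstable patients. They do not remove those just past an episode.
- A reader might infer that recent exacerbations go unrecorded. SOP Step 2 (both procedures) calls for illness history, medications and treating-physician reports, later steps take a medical history, and section 11 keeps outside records. What is missing is a dated item carried into the analysis. Section 12b's list of characteristics is also not worded as exhaustive.
- Referral at a low point is conjecture. Section 11a puts coordinator questions, record retrieval and provider review between referral and treatment, and the baseline test is tied to the treatment date. This delay may reduce the excess at baseline; nothing ensures that it removes it.
- It is tempting to make the main summary only patients with no exacerbation before either test. That selects on a post-treatment event that the protocol hopes treatment will reduce, and dropping patients who are worse at follow-up pushes the mean change upward. With f = 20-30% at each test it would also remove 1 − (1−f)² = 36-51% of patients.

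**Conclusion.** The concern holds as a bias of known direction and unknown size. The entry criteria allow patients recently recovered from a non-ventilated exacerbation, no stable or repeat baseline is required, and an uncontrolled before-after comparison counts any recovery as improvement. Any excess of such patients at baseline over six months raises the mean FEV1 change, and the planned analysis cannot separate that from treatment.

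Under the assumed 10-30% share and 10-25% deficit, the bias runs from 1.1 to 10.0 points with none affected at six months (3.5 at 20% and 15%) down to about 0.1 to 1.8 points with equal shares. These figures rest on full recovery, no treatment effect and no decline. They show that the issue can matter against a 5 to 10% target; they do not show that it produces a result of that size.

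**What to change.** A cheap improvement, with no change to eligibility or treatment:

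1. At the existing history steps (Venous Step 14, Bone Marrow Step 12), record the dates of the last exacerbation, the last hospitalization (ventilated or not) and the last steroid or antibiotic course. Record the same items at six months, for description only.
2. In section 12b, keep the FEV1 change in all patients as the main summary. Add a prespecified summary by baseline status: with or without any such event in a fixed window before the baseline test. The investigators should set the window in advance; the one month already used in 9b is an example.
3. State in advance that an improvement not seen in patients stable at baseline cannot be attributed to treatment.
4. Do not exclude patients for events before the six-month test.

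Cost: a few history items and one extra table. Under the assumed range the stable-baseline group loses 10-30% of patients, leaving 140 to 180 of 200 before any other losses. An interval there would be about 5 to 20% wider (1/√0.9 = 1.05; 1/√0.7 = 1.20). The split shows how far recent exacerbation explains the change; it does not replace a concurrent control.
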